6.3 Determination of sample size

A sample size of 20 participants per treatment group was selected following power calculations and allowing for 10% patient dropout (has dropout rate been factored into our sample size of 20 patients per group). A sample size of 18 patients was calculated for the primary outcome variable (horizontal bone changes) with the assumption that the detectable difference would amount to 0.5mm³ with a standard deviation of 0.5. The type I error probability was set at 0.05 and the statistical power was set at 80%.

6.4 Statistical analyses during the course of the study

The primary and secondary objectives will be analyzed when all data from the 3 month follow-up visit has been collected, entered, verified, and validated (partial clean file).

7 STUDY MANAGEMENT

7.1 Audits and Inspections

Authorized regulatory authorities or an ethics committee may visit the center to perform audits or inspections, including source data verification. The purpose of an audit or inspections is to systematically and independently examine all study-related activities and documents to determine whether these activities were conducted, and data were recorded, analyzed, and accurately reported according to the protocol, ISO 14155, Good Clinical Practice (GCP), guidelines of the International Conference on Harmonization (ICH), and any applicable regulatory requirements.

7.2 Training of staff

The principal investigator will maintain a record of all individuals involved in the study (medical, nursing and other staff). He or she will ensure that appropriate training relevant to the study is given to all of these staff, and that any new information of relevance to the performance of this study is forwarded to the staff involved.

7.3 Changes to the protocol

Study procedures will not be changed without the agreement of the principal investigator.

If it is necessary for the study protocol to be amended, the amendment and/or a new version of the study protocol (Amended Protocol) must be notified to or approved by each Ethics Committee, and if applicable, also the local regulatory authority, before implementation. Local requirements must be followed.

If a protocol amendment requires a change to Informed Consent Form, then the Ethics Committee must be notified. Approval of the revised Informed Consent Form by the Ethics Committee is required before the revised form is used.

7.4 Study timetable

Before a subject's enrollment in the study and any study-related procedures are undertaken the following should be fulfilled:

- Approval of the clinical study protocol
- Approval of the study by the Ethics Committee
- Approval of the study, if applicable, by the regulatory authority

8 ETHICS

8.1 Ethics review

The final study protocol, including the final version of the Informed Consent Form, must be approved or given a favorable opinion in writing by an Ethics Committee as appropriate.

The Principal Investigator is responsible for informing the Ethics Committee of any amendment to the protocol in accordance with local requirements. In addition, the Ethics Committee must approve all advertising used to recruit subjects for the study.

The Principal Investigator is also responsible for providing the Ethics Committee with reports of any SAEs (or ADEs) from any other study conducted with the investigational product.

Progress reports and notifications of SAEs (and ADEs) will be provided to the Ethics Committee according to local regulations and guidelines.

8.2 Ethical conduct of the study

The study will be performed in accordance with ethical principles that have their origin in the Declaration of Helsinki and are consistent with ISO 14155 and ICH/Good Clinical Practice and applicable regulatory requirements.

8.3 Informed consent

The principal investigator(s) will ensure that the subject is given full and adequate oral and written information about the nature, purpose, possible risk and benefit of the study. Subjects must also be notified that they are free to discontinue from the study at any time. The subject should be given the opportunity to ask questions and allowed time to consider the information provided.

The subject's signed and dated informed consent must be obtained before conducting any procedure specifically for the study. The principal investigator(s) must store the original, signed Informed Consent Form in the ISF. A copy of the signed Informed Consent Form must be given to the subject.

8.4 Subject data protection

The Master Informed Consent Form will incorporate (or, in some cases, be accompanied by a separate document incorporating) wording that complies with relevant data protection and privacy legislation. Pursuant to this wording, subjects will authorize the collection, use and disclosure of their study data by the Investigator and by those persons who need that information for the purposes of the study.

The Master Informed Consent Form will explain that study data will be stored in a computer database, maintaining confidentiality in accordance with national data legislation.

9.2 Pregnancy

Many physiologic changes can be observed in the pregnant patient and should be considered when planning dental treatment. It has been suggested to avoid elective dental procedures in the 1st and 3rd trimesters due to risk of spontaneous abortions, pre-term births, increased patient discomfort, and increased likelihood of intraoperative complications (15). The ultimate goal in dental therapy during pregnancy should be to educate the patient on the importance of oral hygiene and plaque control, perform periodontal maintenance therapy and treat emergency situations.

According the American College of Obstetricians and Gynecologists, fetal risks of anomalies, growth restriction, or abortions are not increased with radiation exposures of less than 5 rad (50,000mSv), a level which is well above the range of exposure for diagnostic purposes (16). CBCT radiation exposure levels depends on field of view and manufacturer, and has been shown to fall within the range of 69 to 560 mSv when a medium field of view CBCT was used (17). These dosages are well

below the deterministic threshold for fetal abnormalities as outlined above. Despite the very low risk of adverse pregnancy outcomes, adherence to the ALARA principle or radiology will be adhered to.

Although pregnancy is not a specific exclusion criteria for the study, all potential female subjects of reproductive age will be asked to complete a urine pregnancy test prior to enrollment in the study. Patients who are pregnant at the time of screening will be excluded from the study and referred back to their primary dental provider for further dental treatment. Patients who become pregnant during the course of the study will be asked to notify study personal. As the initial research indicated CBCT would have been completed prior to the patient knowing they were pregnant, and the second CBCT is a standard clinical requirement prior to implant placement, the patient will not be placed at any additional risk if they remained in the study, than if they were not taking part in the study. The patient does have the right to withdraw themselves from the study. Patients will be appropriately educated about the possible effects of dental treatment during pregnancy, along with the effects of ionizing radiation exposure as outlined below.

Pregnancy itself is not regarded as an AE/ADE unless there is a suspicion that the medical device under study may have interfered with the effectiveness of a contraceptive medication.

Congenital abnormalities/birth defects and spontaneous miscarriages should be reported as SAEs. Elective abortions without complications should not be handled as AEs/ADEs.

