3.1.4 Visit 4: Cone Beam Computed Tomography Imaging (12 weeks \pm 7 days)

Small field-of-view cone beam computed tomography (CBCT) imaging whilst wearing the radiographic stent will be obtained for all patients 3 months following surgical treatment. Images will provide post-ridge preservation data for horizontal and vertical bone assessments. Buccal and crestal photographs of the surgical site will be obtained. An elastomeric impression of the site will be obtained.

AEs/ ADEs will be recorded.

This appointment contains a CBCT, photographs and an impression which is standard clinical protocol when planning future implant placement. Additionally the CBCT and impression will be used for research purposes.

Additional visits may be scheduled at the discretion of the investigator and recorded as extra visits in the CRF.

Figure 3 Appointment flow chart

[figure not shown]

Table 1 Study plan

Visit Number	1	2	3	4
Visit Description	Screening, Impressions	Extraction, initial CBCT, Ridge Preservation	Post-op	Post-op, Impressions, final CBCT
Visit Window		0	2w	12w
Patient Information				
Informed consent	X (R)			
Patient demographics	X (C)			
Medical/surgical history	X, (C)			
Oral examination	X (C)			
Inclusion/exclusion criteria	X (R)			
Radiographic examination	X (C)			
Treatment				
CBCT		X (R)		X (C)
Clinical photography		X (C)	X (C)	X (C)
Tooth Extraction		X (C)		
Site Preservation		X (C)		
Suture removal			X (C)	
Impression	X (C)			X (C)
Other				
Adverse events/Adverse device effects		X	X	X
Summary of additional patient requirements per appointment solely for research purposes		CBCT		

**All standard of care procedures will be used for research purposes.

Standard of Care Clinical requirement=C

Research requirement =R

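### Section 9.2 promises no additional risk to a subject who becomes pregnant, but the plan does not ensure that her Visit 4 CBCT is clinically needed then, and 3.1.4 makes no exception

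*Combined protocol and SAP*

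**What the plan says.** Section 9.2 excludes women found pregnant at screening and asks those who become pregnant later to tell the study staff. It then says such a patient "will not be placed at any additional risk if they remained in the study, than if they were not taking part in the study". Two reasons are given. The first CBCT would already have been done before she knew, and "the second CBCT is a standard clinical requirement prior to implant placement".

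The same section advises on dental care in pregnancy ("It has been suggested to avoid elective dental procedures in the 1st and 3rd trimesters") and lists the aims of care as teaching oral hygiene and plaque control, and to "perform periodontal maintenance therapy and treat emergency situations". On imaging it calls the risk very low and says "adherence to the ALARA principle or radiology will be adhered to". It adds: "The patient does have the right to withdraw themselves from the study".

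Section 3.1.4 says the Visit 4 CBCT "will be obtained for all patients 3 months following surgical treatment", in a window of 12 weeks ± 7 days. It calls the scan standard when an implant is being planned and says it also serves research. Table 1 marks this scan C (standard of care) and lists only the Visit 2 CBCT as done solely for research.

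**The concern.** The assurance in 9.2 has no qualification, but the reason behind it has one: the second scan is standard care for someone about to have an implant. For a subject known to be pregnant who has no implant planned, or whose implant can wait, the study calendar rather than her own care may set the date of the scan.

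Two things are at stake: an exposure that could be avoided, against the protocol's own ALARA commitment, and a statement about risk that is firmer than its basis. The comparison of the grafting groups is not at stake.

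**Working it through.** There is no plan figure to reproduce. The check sets the sections side by side.

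1. **What the assurance needs.** The first CBCT is already past when a later pregnancy becomes known, so only the Visit 4 scan matters. Staying in adds no risk if she would have had that scan at about that time anyway.

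2. **How the plan describes the scan.** Table 1 gives a plain C. The text attaches a condition in three places: implant planning (3.1.4), patients who want an implant later (3.3.1) and a coming implant placement (9.2).

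3. **Whether the condition is secured.** The five inclusion criteria in 3.2.2 cover consent, age, physical health, the tooth to be extracted and the adjacent teeth. None requires a planned implant or sets its timing. The exclusion criteria in 3.2.3 do not do so either.

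4. **What fixes the date.** Section 3.1.4 scans everyone 11 to 13 weeks after surgery (12 ± 1). The scan also supplies the 3-month volume for the primary outcome (4.2.1.1.1), so the study has its own reason to keep the date.

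5. **Stage of pregnancy.** Assume conception between Visits 2 and 4, and gestational age equal to time since conception plus 2 weeks. Gestational age at the scan is then at most 13 + 2 = 15 weeks, so mostly first trimester. A conception between the screening test and Visit 2 would add that interval, which the plan does not give.

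6. **What the safeguards allow.**

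| Provision | Effect on the Visit 4 CBCT |
|---|---|
| Notification and education (9.2) | None stated |
| ALARA (9.2) | General commitment, no rule for this scan |
| Withdrawal (9.2) | Avoids the scan by leaving the study |
| Discontinuation, including on safety grounds (3.2.5.1) | Avoids the scan by ending treatment or assessments |
| Procedures after discontinuation (3.2.5.2) | Subject seen if possible and AEs followed; nothing on the scan |

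No row lets her skip or defer the scan and remain in the study.

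7. **Rough scale, for illustration only.** The plan gives no pregnancy rate and no sex or age mix. Assume that 20% to 50% of the 80 subjects could conceive (16 to 40), that the yearly pregnancy rate is 2% to 10%, and that conceptions in the last 4 of 13 weeks are not yet known, which leaves 9 weeks.
   - Probability per subject: 0.02 × 9/52 = 0.00346 to 0.10 × 9/52 = 0.01731.
   - Expected known pregnancies: 16 × 0.00346 = 0.055 to 40 × 0.01731 = 0.692.
   - Chance of at least one: 1 − (1 − 0.00346)^16 = 0.054 to 1 − (1 − 0.01731)^40 = 0.503.

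   The upper end combines both upper assumptions. The count includes all known pregnancies, whether or not the scan is clinically needed, so under these assumptions it overstates the group of concern. The conclusion does not depend on it.

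Two other calculations are left out. A dose comparison would use the range in 9.2, which applies "when a medium field of view CBCT was used"; this study uses a small field, for which no dose is given. A power calculation for a lost volume would have to borrow the difference and SD that 6.3 gives for horizontal bone changes.

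**The case against.** The strongest reply is that the decisive step is not in the documents. The assurance fails only if ordinary care would not scan this patient at about 12 weeks, and no section says so. Table 1 classes the scan as standard of care, 3.3.1 describes people who want implants, and 1.1 and 3.2 frame ridge preservation around later implant placement. The advice on elective care gives reasons that concern procedures, such as complications during surgery; imaging is treated separately and is not advised against. Under 3.2.5.1 assessments can be stopped at any time, and 3.2.5.2 keeps AE follow-up going. The consent pages and a short section just before 9.2 were not available for this review and may say more.

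Most of this stands, and it limits the point. A reader might infer that the Visit 4 CBCT is really a research scan labelled as care, that 9.2 itself calls for imaging to be postponed, or that pregnant subjects are left unprotected. The documents support none of these: the label is explicit and has a stated clinical reason, the advice is about treatment, and several safeguards exist.

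The reply does not close the remaining gap. A general label cannot establish need for a particular patient in a particular week, 3.3.1 is not an eligibility criterion, and every stated way to avoid the scan involves withdrawal or discontinuation.

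**Conclusion.** The point holds as a minor matter of participant protection and wording. Section 9.2 states without condition something that is true only when the second CBCT is clinically needed for that patient at that time. Nothing in the visible protocol ensures this, and 3.1.4 has no exception for known pregnancy.

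That an implant and its planning scan could wait until after the pregnancy is an inference, reasonable but not documented. Few if any subjects would be affected. The fetal risk is very low by the protocol's own account, and the trial's conclusions do not change.

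**What to change.** 1. In 9.2, limit the statement of no additional risk to the case where the second CBCT is clinically needed at that time for that patient.
2. In 3.1.4, with a footnote to the Visit 4 CBCT in Table 1, state that for a subject known to be pregnant the scan is deferred or omitted unless clinically needed then, and that the reason is recorded in the CRF. The impression, photographs and AE recording continue.

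No new missing-data rule is needed. A scan outside the 3.1.4 window counts as missing for the 3-month volume, and 6.1.3 already says that missing data are not estimated.

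The cost is one qualified sentence, one exception and one footnote in a short amendment. The downside is probably no more than one lost primary volume, together with that subject's CBCT-based secondary measurements.
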